#### **Engineering Case Observers**

Engineers from the Sponsor institution may also record technical observations on the device (e.g., recovery pathway from a fault message). These data do not encompass any PHI or PII. These data are intended to support root-cause assessments of product complaints, and future product improvement. These observations are not readily recorded by the investigative site staff, but rather technical subject-matter-experts on the study device. These data are detailed in a memo for this engineering Case Observer survey (

#### **Data Safety Monitoring Plan**

All subjects enrolled in the trial will undergo the procedure that may be considered medically necessary by their physicians. Prior to the procedure, PIs will explain the risks associated with ureteroscopy and percutaneous nephrolithotomy and verify that the research only risks have been explained, and that the subject has signed an informed consent form. There are no anticipated risks, outside of the risk for the standard of care procedures for this clinical trial. All subjects are required to read, understand, and sign the informed consent form associated with the research study. Each subject will be informed of post

procedure symptoms of which to be aware that may represent adverse reactions to the procedure.

The patient will be given oral and written instruction to pay attention to the following.

Upon return to home, the patient will be aware he/her may experience or observe

- mild burning feeling when urinating
- light red stained urine in relation to moderate amounts of blood in the urine
- mild discomfort in the lower abdominal area or flank area when urinating
- the need to urinate more frequently or urgently
- mild discomfort, minimal oozing, or discrete wet feeling at the flank wound site

These problems should settle within one or two days. The patient should call the contact number given by the investigator if bleeding, pain, or discomfort is severe or if problems last more than two days.

The patient should monitor his temperature and reach out the investigator should he/her present with signs of infection:

- Fever above 100 F
- Chills
- Severe burning feeling during urination

The patient should reach out the investigator should he/her present with severe lower urinary signs or symptoms:

- Impossibility to pass urine
- Heavy bleeding in the urine or evacuating clots in the urine
- Heavily blood stained or fluid leakage at the flank wound site

The patient should reach out the investigator should he present with abdominal signs such as:

- Prolonged dizziness, nausea, vomiting
- Feeling bloated and/or does not pass wind for more than 24 hours
- Severe abdominal pain or flank pain

The patient should reach out the investigator should he present with signs that could suggest a deep vein thrombosis:

- Leg pain
- Shortness of breath
- Tachycardia
- Anxiety

If the subject notes any of these symptoms, he/she is instructed to contact his/her physician, who will determine the course of action. All events are to be reported within 48 hours of occurrence to the coordinating site. All adverse events (AEs) will be reviewed by the medical monitor within one month of their occurrence and summarized for review. The PI will be responsible for submitting this report to the IRB at his/her institution as required. AEs and other reportable events are defined above in Section 8.

Printed copies are considered UNCONTROLLED documents after the date printed. Printed on September 17, 2024. CONFIDENTIAL, PROPRIETORY OF AURIS HEALTH, INC

	PROTOCOL	Doc #:	104-010990-00
	First-in-Human Study Protocol – Monarch Urology	Rev:	С
AURIS	(Protocol No.: 2021-URO-0001)	Page:	38 of 48

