#### **Criteria for Terminating Study**

Sponsor reserves the right to terminate the study but intends only to exercise this right for valid scientific or administrative reasons and reasons related to protection of patients. Investigators and associated IRB will be notified in writing in the event of termination.

Possible reasons for study termination include:

- The discovery of an unexpected, significant, or unacceptable risk to the patients enrolled in the study.
- The occurrence of any device-related death or device-related serious adverse event causing permanent injury.
- A decision on the part of Sponsor to suspend or discontinue development of the device.

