#### Criteria for Suspending/Terminating a Study Center

Sponsor reserves the right to stop the study center at any time after the study initiation visit if no patients have been enrolled or if the center has multiple or severe protocol violations without justification or fails to follow remedial actions.

Possible reasons for suspending/terminating a study center include:

- Repeated failure to complete case report forms prior to scheduled monitoring visits.
- Failure to obtain written Informed Consent.
- Failure to report CEC Events/SAE/UADE to the study Sponsor within 24 hours of knowledge.

	PROTOCOL	Doc #:	104-010990-00
	First-in-Human Study Protocol – Monarch Urology	Rev:	С
AURIS	(Protocol No.: 2021-URO-0001)	Page:	22 of 48

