  - the adverse event does not follow a known response pattern to the medical device (if the response pattern is previously known) and is biologically implausible;
  - the discontinuation of medical device application or the reduction of the level of activation/exposure when clinically feasible -
  - and reintroduction of its use (or increase of the level of activation/exposure), does not impact on the adverse event;
  - the event involves a body-site or an organ that cannot be affected by the device or procedure;
  - the adverse event can be attributed to another cause (e.g. an underlying or concurrent illness/ clinical condition, an effect of another device, drug, treatment or other risk factors);
  - Harms to the subject are not clearly due to use error; or

In order to establish the non-relatedness, not all the criteria listed above might be met at the same time, depending on the type of device/procedure and the adverse event.

- **Possible:** The relationship with the use of the investigational device or comparator, or the relationship with procedures, is weak but cannot be ruled out completely. Alternative causes are also possible (e.g. an underlying or concurrent illness/ clinical condition or/and an effect of another device, drug or treatment). Cases where relatedness cannot be assessed, or no information has been obtained should also be classified as possible.
- **Probable:** The relationship with the use of the investigational device or comparator, or the relationship with procedures, seems relevant and/or the event cannot be reasonably explained by another cause.
- **Causal:** The serious adverse event is associated with the investigational device, comparator or with procedures beyond reasonable doubt when:
  - The event is a known side effect of the product category the device belongs to or of similar devices and procedures;
  - The event has a temporal relationship with the device uses/application or procedures;
  - The event involves a body-site or organ that:
    - The device or procedures are applied to or is adjacent to;
    - The device or procedures have an effect on;
  - The event follows a known response pattern to the medical device (if the response pattern is previously known);
  - The discontinuation of medical device application (or reduction of the level of activation/exposure) and reintroduction of its use (or increase of the level of activation/exposure), impact on the event (when clinically feasible);

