#### 8.2 General Reporting Requirements (Serious & Non-Serious Adverse Events)

All adverse events must be recorded on the Adverse Event CRF by the Investigator (or designee). The report should include: severity, duration, action taken, treatment outcome and relationship of the adverse experience to the study device, procedure, concomitant medications, pre-existing condition, etc. (i.e., unrelated, related or relationship unknown). The investigative site will report non-serious adverse events into the electronic clinical database within 1 week after they become aware of the non-serious adverse event.

In the case of serious adverse events, procedure and/or device observations and malfunctions, de-identified medical record documentation (e.g. procedure notes, operative notes, discharge summary, relevant progress notes, imaging or lab studies) must be provided to study sponsor or its designee.

The following criteria must also be adhered to by the Investigator in the case of serious adverse events:

- The Adverse Event CRF must be signed by the Investigator or Co-Investigator.
- It is the responsibility of the Investigator to inform their IRB of serious adverse events as required by their IRB procedures and in conformance with FDA and local regulatory requirements.

All serious adverse events must be reported by the Investigator (or designee) to the Sponsor, within 24 hours of learning of the adverse event via CRF. The Sponsor contact information for questions is:

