# **13.** Data Handling and Recordkeeping

Standardized electronic CRFs will be utilized by the participating site using a standardized database. Electronic data capture system will be used in this study. Investigator is responsible for the accurate completion and timely submission of the data collected during the Study. Incoming data will be monitored by the Sponsor or designee to identify inconsistent or missing data and any adverse events. Any data issues are to be promptly addressed with the investigator. Quality assurance procedures will be established to ensure that complete, accurate and timely data are submitted, that protocol requirements are followed, and that complications, adverse events and adverse device effects are correctly reported and investigated, as appropriate. Investigator is to maintain all source documents as required by the protocol, including laboratory results, supporting medical records, and signed Informed Consent Forms and HIPPA authorization forms. The source documents will be used during the regular monitoring visits to verify information from the database against data contained on the completed CRFs.

The Principal Investigator must maintain detailed records on all subjects who sign the Informed Consent and begin the pre-procedure evaluation. Data for enrolled subjects will be entered into CRFs provided by the Sponsor. All data should be entered completely, promptly, and legibly. For source documents, corrections should be made in a manner that does not obscure or eliminate the original error, by striking through the original data with one line, and initialing and dating the change, along with the reason for the change (if not obvious).

Study Exit CRFs are completed for all enrolled subjects, regardless of if they did or did not complete the Study (e.g., subject discontinuation, Study termination).

The PI will review the results, and the results will become part of the subject's medical record and research record. Any clinical follow-up or repeat procedures will be dictated by the patient's physician based on clinically relevant data and will not be influenced by enrollment into this study. All patient information will be de-identified. All information and data related to this study will be stored in a secured, locked cabinet in a secure office accessible only by the PI.

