#### Monitoring [21 CFR 812. 46]

Sponsor or its designee will conduct investigational site monitoring to ensure that all Investigators are in compliance with the protocol and the Investigators' agreements. The sponsor and/or designee will monitor the site to ensure that the completed Case Report Forms match the medical records, and resolve any differences. The sponsor will retain the right to remove either the Investigator or the investigational site from the study.

The sponsor will review significant new information, including unanticipated serious adverse events and ensure that such information is provided to the Investigators and to all reviewing IRB.

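### The medical monitor has the same one-month limit for serious and non-serious adverse events, and no dated medical review of a serious event beyond the treating site is required before the next case

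*Protocol*

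**What the plan says.** - **Medical review.** Protocol section 13, Data Safety Monitoring Plan: "All adverse events (AEs) will be reviewed by the medical monitor within one month of their occurrence and summarized for review". This is the only mention of the medical monitor. The same paragraph sends all events to the coordinating site within 48 hours of occurrence and makes the investigator responsible for passing the resulting report to the IRB.
- **Reporting.** Section 8.2 has the investigator report SAEs to the Sponsor "within 24 hours of learning of the adverse event" and enter non-serious events in the database within 1 week of awareness. For SAEs, de-identified medical records must also go to the Sponsor or its designee, with no date attached.
- **Sponsor oversight.** Section 13: "Incoming data will be monitored by the Sponsor or designee to identify inconsistent or missing data and any adverse events". Appendix II, Monitoring: "The sponsor will review significant new information, including unanticipated serious adverse events and ensure that such information is provided to the Investigators". Neither carries a deadline.
- **Stopping.** Section 4.2, Criteria for Terminating Study, gives the Sponsor a right to terminate. The possible reasons include "The discovery of an unexpected, significant, or unacceptable risk to the patients enrolled in the study" and "The occurrence of any device-related death or device-related serious adverse event causing permanent injury". No pause or spacing between cases is described.
- **Committees.** SAP section 9 says that there was no data monitoring committee. The study-center criteria in section 4.2 list "Failure to report CEC Events/SAE/UADE to the study Sponsor within 24 hours of knowledge", which names CEC events, but the readable text describes no CEC process.
- **Attribution.** Section 8.1 leaves identification and classification of events to the site investigator. It lists events thought unlikely to be device-specific, among them visceral injury from percutaneous access, major bleeding and renal fracture. The list is expressly guidance, and section 8.1 also says: "Cases where relatedness cannot be assessed, or no information has been obtained should also be classified as possible".

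**The concern.** The protocol separates serious from non-serious events when they are reported, but not when they are medically reviewed. After the 24-hour report, no step with a date requires anyone beyond the treating site to judge what happened and whether the next case should go ahead. Every party can comply in full while further patients are treated before that judgement is due.

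This matters more than usual here. It is a first-in-human series at one site, and the only earlier evaluation of the procedure that the protocol describes is in porcine models. The first relatedness judgement belongs to the treating site. Several events that section 8.1 lists as unlikely to be device-specific can arise from the percutaneous step, yet in section 4.2 the study device's electromagnetic guidance directs the needle. One of the listed termination reasons turns on device-relatedness. These are the events for which a prompt second medical opinion is most useful.

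**Working it through.** The documents give no number of cases treated before monitor review, and the sample size has no statistical basis, so there is no figure of the plan's own to reproduce. The check has two parts.

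**1. The time limits side by side**

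| Step | Serious | Non-serious | Counted from |
|---|---|---|---|
| Report to coordinating site (section 13) | 48 hours | 48 hours | occurrence |
| Report to Sponsor, or database entry (8.2) | 24 hours | 1 week | awareness |
| Records to Sponsor (8.2) | required, undated | not required for the event alone | none |
| Sponsor monitoring and review (13, Appendix II) | undated | undated | none |
| Medical monitor review (13) | one month | one month | occurrence |
| Pause before next case | none stated | none stated | none |

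The first two rows are duties to report. The only dated review beyond the site is the monitor's, and it is not tiered.

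**2. Cases treated before the review falls due**

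Inputs: up to 20 patients and up to 16 weeks of enrolment (section 4.2, Sample size); one center (section 4.2); one month taken as 28 to 31 days.

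- Planned rate: 20 / 16 = 1.25 cases per week.
- Further cases = rate × days / 7, for an SAE known on the day it occurs: 1.25 × 28/7 = 5.00; 1.25 × 30/7 = 5.36; 1.25 × 31/7 = 5.54.
- SAE first known on day 7, so that 21 to 24 days remain: 1.25 × 21/7 = 3.75; 1.25 × 24/7 = 4.29.
- Late in the series fewer patients remain. If the SAE is in case k, the count is min(x, 20 − k). Averaged over k = 1 to 20: 85/20 = 4.25 for x = 5.00; 90/20 = 4.50 for x = 5.36; 92.5/20 = 4.63 for x = 5.54.
- Uneven timing. If the other 19 cases fall at random over 112 days and a full 30-day window lies within enrolment, the mean is 19 × 30/112 = 5.1, and the binomial probability of 6 or more is 0.40.
- Other accrual rates (assumed), over 30 days: 15 in 16 weeks gives 15/16 × 30/7 = 4.02; 20 in 12 weeks gives 20/12 × 30/7 = 7.14.

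**3. With a 72-hour review**

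- No hold, 24 hours to report plus 72 hours to review = 4 days: 1.25 × 4/7 = 0.71 cases (0.54 at 15 in 16 weeks; 0.95 at 20 in 12 weeks).
- Delay from one 72-hour hold: 1.25 × 3/7 = 0.54 of a case (0.40; 0.71).

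**The case against.** The strongest reply is that the SAE response runs through section 8.2, not through the monitor. The Sponsor is told within a day of awareness, is to receive operative notes, imaging and laboratory results, and can terminate. The sentence about the monitor can be read as a periodic summary step, since it leads to a report for the IRB. Sponsor engineers may record technical observations on the device, the IRB is to be told of SAEs, and IRB or regulatory deadlines may exist in rules that the protocol only refers to. A CEC may be described outside the readable text.

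Most of this stands, and it limits the point. It does not close the gap: section 8.2 dates the report but neither the record package nor an assessment, and the Sponsor's review has no deadline. If the monitor's month is only a summary step, then no dated medical review beyond the site is left at all.

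Four stronger readings are tempting, but the documents do not support them:

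- *Nobody beyond the site knows of an SAE, or can act on it, for a month.* The 24-hour report and the right to terminate rule this out.
- *Five cases is the most the plan allows.* It is an average at the planned pace. Enrolment may take less than 16 weeks and no case spacing is stated, so the plan sets no maximum.
- *The section 8.1 list keeps access injuries from being treated as device-related.* The list is guidance, the investigator may decide otherwise, unassessable events are graded as possible, and termination for an unacceptable risk does not depend on relatedness.
- *There is no safety oversight.* Oversight is described; what is missing is a date for one part of it.

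**Conclusion.** The point holds in a limited form. The monitor's limit should be tiered by seriousness, as reporting already is. At present no readable text dates a medical assessment of an SAE beyond the treating site, or requires one before the next case.

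About 5 further cases (5.0 to 5.5) would on average be treated before the review falls due, a quarter of the planned 20. The average is 4.3 to 4.6 if the SAE is equally likely in any case of the series. These figures assume even accrual of 20 patients over the full 16 weeks and an SAE known on the day it occurs. They count cases before a deadline, not before the Sponsor knows, and a monitor who reviews early would reduce them. Assumed accrual rates move the 30-day figure between 4.0 and 7.1.

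This is a cheap safety improvement. It does not affect the validity of the descriptive results. The SAP, dated 08DEC2023, refers to the data monitoring committee and to the data summaries in the past tense, so conduct may have been well advanced. That bears on when the change can be applied, not on whether the gap is there.

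**What to change.** Amend the Data Safety Monitoring Plan in Protocol section 13:

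1. For SAEs and unanticipated adverse device effects, the existing medical monitor reviews the event and records a relatedness grade within a short limit, for example 72 hours, of receipt of the section 8.2 report. This includes events on the section 8.1 list.
2. For a death, or an SAE at least possibly device-related that causes permanent injury, no new study case starts from the Sponsor's receipt of the report until the medical monitor and the Sponsor have documented an assessment against the termination reasons in section 4.2. That assessment is due within the same limit. Other SAEs need no hold.
3. The limit of one month from occurrence stays unchanged for non-serious events. Counting it from awareness would loosen it for events recognised late.

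The 72 hours is a suggestion; the documents give no basis for a particular figure. The cost is protocol wording, a faster turnaround from the monitor for every SAE, and about 0.5 of a case delayed per 72-hour hold (0.4 to 0.7 over the assumed accrual rates). The protocol does not document the monitor's availability, so the Sponsor should confirm that the limit can be met or name a deputy. Without a hold, the average number of cases treated between awareness and review would be about 0.7 (0.5 to 1.0).

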## **14.** Monitoring

Monitoring visits to the clinical site will be made periodically during the study by the Sponsor's designee to ensure that all aspects of the current, approved protocol/amendment(s) are followed. Original source documents will be reviewed for verification of data in the database. The Investigator/institution guarantees direct access to original source documents by Sponsor, Sponsor's designees, and appropriate regulatory authorities. In the event that the original medical records cannot be obtained for a patient that is seen by a non-study physician at a non-study institution, photocopies of the original source documents must be made available for review.

It is important that the Investigator and relevant study personnel are available during the monitoring visits and that sufficient time is devoted to the process.

Phone contacts and site visits will be conducted to ensure that the protocol is being followed and that any protocol deviations are properly documented. Clinical monitoring will include a verification that Informed Consent was properly obtained for all enrolled study participants, a review of clinical records for accuracy and completeness, resolution of missing or inconsistent results and a review of source documents. The clinical monitor will verify that the CRFs are in agreement with the source documentation and other records. The investigator will make available to the clinical monitor for review all Informed Consent documents, source documentation, original laboratory data and other relevant records for all enrolled subjects at the site. It is important that the investigator and other relevant site personnel are available for consultation with the clinical monitors during the monitoring visits and that sufficient time is devoted at the site to the monitoring process.

Additionally, telephone and/or e-mail contact will be conducted on a regular basis with the investigator and the site staff to ensure that the protocol is being followed and to address any issues that may occur during the course of the Study.

If a deficiency is noted during an on-site visit (or at any other time during the course of the Study), the clinical monitor is required to discuss the situation with the investigator and the Sponsor (if required) to secure compliance.

